## 8. EFFICACY ASSESSMENT

### 8.1. Specification of Efficacy Parameters

- **Primary outcome:** the number of COPD exacerbations due to infectious episodes diagnosed by the clinician in charge.
- **Secondary outcomes:**
  - Rate of COPD exacerbations per patient included in the study.
  - Decrease in the severity of the COPD exacerbations.
  - Time elapsed between the start of the treatment and the first COPD exacerbation.
  - Use of drugs (antibiotics, corticosteroids, etc).
  - Number of medical consultations due to COPD exacerbations.
  - Number of hospitalizations due to COPD exacerbations.
  - Days of hospitalization due to COPD exacerbations.
  - Number of visits to the Emergency Department resulting or not in hospitalization.
  - Health-related quality of life, as determined by an adapted version of the specific CAT test.
  - Ratio between the number of COPD exacerbations and the healthcare expenditure resulting from resource consumption during episodes of COPD exacerbations occurring during the trial period.

- Variations (change between the baseline level and months 0, 3, 6, and 12, as well as in comparison with the placebo) in the immunological parameters described in page 63.
- Safety outcomes:
  - ~ Overall rate, severity, and relationship of any adverse event per administration and patient.
  - ~ Assessment of local tolerability (tissular reactions in the administration site).
  - ~ Changes in standard laboratory parameters (serum chemistry and hematology).

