To compare the change in the immunological variables described in the trial design (page 67) at 0, 3, 6, 12, and 18 months, an analysis of covariance will be performed, estimating the mean difference over time in both study groups.

The cost-benefit ratios in the study groups will be estimated together with their 95% CI, and compared using non-parametric tests.

The safety variables will be compared using the chi-square test in the case of qualitative variables or Student's T test in the case of quantitative variables whenever they meet parametric assumptions, or using non-parametric test in the opposite case.

The statistical software that will be used is STATA 11.

---

**10.2. Number of Anticipated Subjects and Rationale. Calculation Method Used for Determining the Sample Size and Data Used for Such Purpose**

The calculation of the sample size is based on the efficacy measured based on the decrease in the number of episodes of COPD exacerbations during the 12-month treatment period of the trial per subject.

The ratio of subjects to be distributed among the active treatment and placebo groups will be 1:1.

We estimate that subjects from group I (active treatment with the bacterial vaccine) will achieve a 60% decrease in their number of COPD exacerbations compared with a 30% decrease among those of group II (placebo). With an alpha error of 0.05 and a beta error of 0.2, and assuming a dropout rate of 20-25%, the number of subjects to be recruited would be 90 per study group, with an overall total of 180 trial subjects.

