6.1.2. Secondary outcomes

- ★ Decrease in the rate of COPD exacerbations per study group at 12 months (end of the trial treatment) and 6 months after the trial's termination (follow-up).
- ★ Decrease in the severity of the COPD exacerbations. The severity of the exacerbations will be measured based on the consumption of healthcare resources (i.e., visits to the Emergency Department, hospitalizations, or consultations), as follows:
 - ICU hospitalization: 4 points.
 - Standard hospitalization: 3 points.
 - Emergency Department visit: 2 points
 - Consultation involving a change in the patient's usual treatment: 1 point.
- ★ Time elapsed between the start of the treatment and the first COPD exacerbation
- ★ Use of drugs (antibiotics, corticosteroids, etc). Drug consumption will be scored as follows:
 - Use of antibiotics: 1 point.
 - Use of inhaled corticosteroids: 2 points.
 - Use of systemic corticosteroids: 3 points.
 - Use of oxygen therapy: 4 points.
 - Use of mechanical ventilation: 5 points.
- ★ Number of hospitalizations due to COPD exacerbations.
- ★ Days of hospitalization due to COPD exacerbations.
- ★ Number of visits to the Emergency Room.
- ★ Number of unscheduled medical consultations due to COPD exacerbations.
- ★ Health-related quality of life, as determined by an adapted version of the specific CAT test.
- ★ Healthcare expenditure resulting from resource consumption during episodes of COPD exacerbations occurring during the trial period.
- ★ Variations (change between the baseline level and months 0, 3, 6, and 12, as well as in comparison with the placebo) in the following immunological parameters in the patients participating in the immunological substudy (N = 60) and/or those of the subgroup of the induced sputum study (N = 20) (between month 0 prior to the administration of the vaccine and month 12).

In the case of patients participating in the IMMUNOLOGICAL SUBSTUDY (n = 60), changes in the below parameters will also be assessed during the randomization visit (visit 1) and the visits corresponding to months 3, 6, and 12:

- The specific humoral response [REDACTED]
- The in vitro proliferative response of specific T cells [REDACTED]

In a subgroup of patients (n = 20) selected from the group of patients participating in the immunological substudy (n = 60), the following parameters will also be evaluated in samples of induced sputum at month 0 (visit 1) and month 12:

- ★ IgA response to Bactek antigens assessed using ELISA technique.

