7.1.9. Model Assumptions

Primary endpoint analysis will use a median test or a Mann-Whitney test. Secondary endpoints will use relevant tests (Fisher's exact, T test, etc.) and a Poisson regression for exacerbations with baseline characteristics as covariates.

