7.4.2. Secondary Efficacy Analysis

The following variables will be analyzed to determine whether they follow a normal distribution: number of exacerbations, duration of the episodes, need for antibiotic therapy, number of hospital admissions, duration of the hospital admissions, immunological outcomes described in the trial design, quality of life, and direct costs.

These variables will be described together with their mean and standard deviation, or, in case of asymmetry, with their median and interquartile range. Differences between the means will be analyzed using Student's T test in the case of variables with a normal distribution and Mood's median test in the case of variables without a normal distribution. The absolute effect (difference in estimators) and its precision will be estimated with a 95% confidence interval (CI) in all cases.

The appearance of the first exacerbation will be studied at 3, 6, 12 months and whole study in the intention to treat (ITT) and per protocol (PP) sets and these same limits will be studied in the moderate and severe COPD populations. The appearance of any exacerbation at 3, 6, 12 months and whole study will be studied in the ITT and PP sets.

Number of exacerbations will be studied in the mild, moderate and severe COPD populations at 3, 6, 12 months and whole study. Number of exacerbations in the ITT and PP sets will be studied at 3, 6, and 12 months.

To compare the change in the immunological variables described in the trial design at 0, 3, 6, 12, and 18 months, an analysis of covariance will be performed, estimating the mean difference over time in both study groups.

The cost-benefit ratios in the study groups will be estimated together with their 95% CI, and compared using non-parametric tests.

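### Skewed costs are sent to a median test and cost-benefit ratios to unnamed non-parametric tests, so no contrast of mean cost is planned for an expenditure outcome

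*SAP*

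**What the plan says.** SAP 6.1.2 lists the economic outcome as "Healthcare expenditure resulting from resource consumption during episodes of COPD exacerbations occurring during the trial period". Two rules in SAP 7.4.2 bear on it, and protocol 10.1 has both.

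- **Direct costs.** These are among the variables to be checked for normality. If normal, they get Student's t test; if not, "Mood's median test in the case of variables without a normal distribution". The description switches too: "in case of asymmetry, with their median and interquartile range". The section adds: "The absolute effect (difference in estimators) and its precision will be estimated with a 95% confidence interval (CI) in all cases".
- **Cost-benefit ratios.** "The cost-benefit ratios in the study groups will be estimated together with their 95% CI, and compared using non-parametric tests". No test is named.

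The SAP does not define the ratio. The only description of one is in protocol 8.1: "Ratio between the number of COPD exacerbations and the healthcare expenditure resulting from resource consumption during episodes of COPD exacerbations". Elsewhere, SAP 7.1.9 says "Primary endpoint analysis will use a median test or a Mann-Whitney test". Mood's test and Mann-Whitney are the only non-parametric two-group tests that either document names for quantitative outcomes. Neither mentions a bootstrap, a permutation test of means or a regression model for costs.

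**The concern.** Expenditure adds up. What a payer saves is the difference in mean cost times the number of patients, so an economic conclusion rests on arithmetic means. Exacerbation costs are likely to be strongly skewed: many patients with little or no cost and a few with an expensive admission. They would then fail the normality check, and the plan would move them to medians. The difference in estimators with its 95% interval becomes a difference in medians, and the p-value comes from Mood's test. Neither measures expenditure.

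The mismatch can run both ways. Admissions drive the mean but move few patients past the median or far up the ranks. Cheap consultations do the reverse. Admissions, hospital days and consultations are separate secondary outcomes here, so the trial itself allows for the event mix to change. The cost conclusion could then disagree with the money spent.

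**Working it through.** The documents give no figure for the economic comparison, so there is none to reproduce. They do give the arm size, 90 per group with 20-25% dropout (SAP 7.1.1; 90 × 0.75 = 67.5, about 68), and alpha 0.05 (protocol 10.3), taken here as two-sided. All unit costs, event rates and dispersions below are assumptions.

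**Inputs, first set.** Placebo has 1.7 non-hospital exacerbations a year at EUR 120 each and 0.40 hospital exacerbations at EUR 3,500 each. Counts are negative binomial (dispersion 0.8 and 1.5). Event costs are gamma (shape 2 in the check).

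Mean cost = (non-hospital rate × 120) + (hospital rate × 3,500).

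- Placebo: 1.7 × 120 + 0.40 × 3,500 = 204 + 1,400 = EUR 1,604.
- Equal mean cost, different mix: non-hospital rate 0.9. The 0.8 × 120 = EUR 96 saved is offset by 96 / 3,500 = 0.027 more admissions. Then 0.9 × 120 + 0.427 × 3,500 = 108 + 1,494.5, about EUR 1,602.
- Admissions only, 0.40 to 0.10: 204 + 350 = EUR 554, a saving of EUR 1,050 per patient.

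Share of simulated trials with p < 0.05 on per-patient cost, 90 per arm:

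| Scenario | Mann-Whitney | Mood | Welch (means) |
|---|---|---|---|
| Identical distributions | 5-6% | about 2.5% | 5-6% |
| Equal mean cost, different mix | 26% | 23% | 5% |
| Admissions only, 0.40 to 0.10 | 57% | 23% | 86% |

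With 68 per arm the admissions-only row becomes 47%, 18% and 74%.

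**Second set, 68 per arm.** This set uses 150 cost units per outpatient episode, 3,000 per admission, lognormal costs and dispersion 0.6.

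- Equal mean cost (about 910 in each arm; 1.2 against 2.1 exacerbations, with a larger share admitted in the arm with fewer): Mann-Whitney 34%, Mood 31%, Welch 4%.
- Admitted share down from 10% to 2% (mean 915 to 438): 12%, 3% and 56%.
- Over dispersion 0.3-1.0 and admission cost 1,500-6,000, the equal-cost rates were 23-48%, 21-42% and 4-5%. The power figures were 8-14%, 3-4% and 34-69%.

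**The ratio.** Using the description in protocol 8.1 and the first set's equal-cost scenario:

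- Active: (0.90 + 0.427) / 1,602 = 0.83 exacerbations per EUR 1,000.
- Placebo: 2.1 / 1,604 = 1.31 per EUR 1,000.

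The arm ratios therefore differ although mean cost does not. A per-patient ratio is also undefined for anyone with no exacerbation, which was 19-46% of patients per arm in the second set.

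**The case against.** The strongest reply is that the quoted sentence is about ratios, while the simulations are about cost. This stands. In the equal-cost scenario the arms' exacerbation-to-expenditure ratios truly differ, so a reader might take 26% as a false-positive rate for the planned ratio comparison, and it is not one. Applied to per-patient ratios in patients with at least one event (first set, 90 per arm), Mann-Whitney rejected in 14-16% of trials in that scenario and had 62% power for the admissions-only fall. The rejection rates above belong to the direct-costs rule, where a median test is prescribed by name.

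Other replies also have force:

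- **The ratio test is not named.** A patient-level bootstrap is itself non-parametric, so "compared using non-parametric tests" could cover one. That the ratios will get a rank or median test is an inference from the tests named elsewhere.
- **Rank tests are not always weaker.** If all exacerbations fall in proportion, Mann-Whitney has about 72-76% power at 90 per arm, against about 40% for the comparison of means. That is close to the effect the trial plans for.
- **A vaccine that only prevents cheap consultations.** A reader might infer that one saving nothing would often be called cost-saving. That case was not simulated. Preventing 0.8 consultations at EUR 120 does save EUR 96, and the means are equal only because admissions were added.
- **Calibration.** The annual EUR 1,652-2,344 per patient in protocol 3.1 follows a sentence on social, occupational and healthcare costs together. The outcome is expenditure during exacerbations only, so that range does not validate the assumed unit costs.
- **Safeguards.** An interval accompanies the ratio, and SAP 7.1 says that no significance levels are used, though protocol 10.3 sets 0.05. The interval belongs to an undefined ratio, and the interval for skewed direct costs is for medians, so neither supplies the difference in mean cost.

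**Conclusion.** The point holds for costs. Followed as written, skewed direct costs get a median contrast and Mood's test, and no test or interval for mean cost is planned. In plausible but assumed settings, rank and median tests rejected equal mean cost in 21-48% of trials. Mood's test, the one prescribed for non-normal costs, had 3-23% power for a large saving from admissions alone (a 75% fall in the first set, 80% in the second), where Welch's test had 34-86%. The sizes depend on unit costs that the documents do not give; the direction was the same in both sets of assumptions.

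For the ratios the supportable charge is narrower: the quantity is undefined in the SAP and the test is unnamed. The documents do not support calling the planned test wrong for the ratio at any stated error rate, nor calling it generally weak. The outcome is secondary, so the consequence is confined to the economic conclusion.

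**What to change.** Make the same changes in SAP 7.4.2 and protocol 10.1:

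1. Remove direct costs from the list governed by the t test or Mood's-median rule. If this is left out, the new text will contradict the same section.
2. Add: *Arms will be compared on arithmetic mean cost per patient over the same period, by the difference in means with a patient-level bootstrap 95% confidence interval.*
3. Define the ratio in the SAP, and replace the non-parametric comparison with: *Any cost-benefit or cost-effectiveness ratio will be computed from arm-level means, with costs and exacerbations resampled jointly by patient, and reported with the resulting 95% interval. Any rank or median test on costs is descriptive only.*

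The cost is wording and a few lines of Stata or R, both already in the SAP's software list. No new data are needed. There are two downsides. The interval will be wide and slightly liberal at 70-90 per arm: in the equal-cost scenario the bootstrap rejected in 6-8% of trials. And if all exacerbations fall in proportion, the comparison of means gives up power to Mann-Whitney (about 40% against 72-76% at 90 per arm).

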7.5. Safety Evaluation

All adverse events of the trial will be coded according to MedDra classification. MedDra version will be communicated in the statistical report. The safety variables will be compared using the chi-square test in the case of qualitative variables or Student's T test in the case of quantitative variables whenever they meet parametric assumptions, or using non-parametric test in the opposite case. AEs will be summarised by System Organ Class and Preferred Term displaying number of subjects, number and percentage of subjects having the event as well as number of events. Furthermore, the AEs will be summarised according to severity, relationship, outcome and seriousness.

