**10.3. Significance Level to be Used**

The significance level for the efficacy assessment will be 0.05 for a type I error ( $\alpha$ ) and 0.2 for a type II error ( $\beta$ ).

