HGUGM	Hospital General Universitario Gregorio Marañón
HCSC	Hospital Clínico San Carlos
CRF	Case Report Form
CAT	COPD ASSESSMENT TEST
ELISA	Enzyme Linked ImmunoSorbent Assay
GCP	Good Clinical Practice
IgAs	Secretory Immunoglobulin A
IMP	Investigational Medical Product
ITT	Intention To Treat Set or Population
LNs	Local/regional mucosa-draining lymph Nodes
MALT	Mucosa-Associated Lymphoid Tissue
NKs	Natural Killer cells
PHA	Phytohemagglutinin
PIDs	Primary ImmunoDeficiencies
PP	Per Protocol Set or Population
RRTIs	Recurrent Respiratory Tract Infections
SAE	Serious Adverse Event
SAP	Statistical Analysis Plan
SUSARs	Suspected Unexpected Serious Adverse Reactions

1. *Revisions*

2. *Introduction*

2.1. *Preface*

This statistical analysis plan (SAP) describes all planned analyses for the Clinical Study Report (CSR) of study MV130-SLG-001, a prospective, randomized, double-blind, parallel, placebo-controlled clinical trial evaluating the safety, clinical efficacy, and immunomodulatory response of a polyvalent bacterial vaccine (Bactek[®]) administered via the sublingual mucosa in subjects with chronic obstructive pulmonary disease (COPD).

The content of this SAP is based on protocol MV130-SLG-001 Amendment version 8. All decisions regarding final analysis, as defined in the SAP document, have been made prior to database lock of the study data.

Other endpoints, including immunological substudies, as well as other potential future analyses of data arising from this trial, will be the subject of future analysis plans.

2.2. *Scope of the analyses*

These analyses will assess the efficacy and safety of MV130 in comparison with placebo and will be included in the clinical study report. This statistical analysis plan (SAP) will give more detailed descriptions of the endpoints in the study and the corresponding analyses.

3. Trial Objectives

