7.1.1. Sample Size and Power

The calculation of the sample size is based on the efficacy measured based on the decrease in the number of episodes of COPD exacerbations during the 12-month treatment period of the trial per subject.

The ratio of subjects to be distributed among the active treatment and placebo groups will be 1:1.

We estimate that subjects from group I (active treatment with the bacterial vaccine) will achieve a 60% decrease in their number of COPD exacerbations compared with a 30% decrease among those of group II (placebo). With an alpha error of 0.05 and a beta error of 0.2, and assuming a dropout rate of 20-25%, the number of subjects to be recruited would be 90 per study group, with an overall total of 180 trial subjects.

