7.1.5. Multiple Comparison

If multiple comparisons are needed, Holm adjustment for multiple comparisons will be used. However, the analysis will try to obviate multiple comparisons except as exploratory analysis.

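### Adverse-event proportions are compared by chi-square test and counts only, with no confidence interval for the difference, so at 90 per arm a non-significant result says little about safety

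*SAP*

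**What the plan says.** SAP 2.2 sets the aim: "These analyses will assess the efficacy and safety of MV130 in comparison with placebo". For categorical safety data, SAP 7.5 carries this out as follows: "The safety variables will be compared using the chi-square test in the case of qualitative variables". Protocol 10.1 has the same sentence. Quantitative safety variables get a t test or a non-parametric test.

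SAP 7.5 also plans tables by System Organ Class and Preferred Term, with numbers and percentages of subjects affected and numbers of events, and summaries by severity, relationship, outcome and seriousness. Protocol 9.2 asks for its adverse-event tables by treatment group.

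Neither section names a contrast between arms or an interval for it. Efficacy is treated differently. SAP 7.4.1 attaches 95% intervals to relative risks and the hazard ratio, and SAP 7.4.2 attaches them to absolute effects and cost-benefit ratios.

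The only significance level in the protocol is for efficacy: "The significance level for the efficacy assessment will be 0.05 for a type I error" (protocol 10.3). The sample size rests on exacerbations: "the number of subjects to be recruited would be 90 per study group" (SAP 7.1.1).

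**The concern.** A chi-square p-value shows whether the data are surprising if there is no difference. It does not show how large a difference the data still allow. In a trial sized for efficacy, that second question is the useful one for safety, because most uncommon events will give p > 0.05 whether or not the product raises their frequency. As planned, the report will contain percentages without precision and a test that often cannot distinguish no excess from a doubling. What is at stake is how far the report can support a statement about safety against placebo, which SAP 2.2 sets as an aim.

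**Working it through.** **Inputs.**
- 90 per arm, 1:1 (SAP 7.1.1).
- Safety denominator: randomized subjects with at least one dose (protocol 10.7); SAP 5.1.1 says all randomized subjects. Both give about 90 per arm, not completers only.
- Two-sided alpha of 0.05: assumed, since no level is set for safety.
- Event rates: assumed, 5% doubling to 10% and 10% doubling to 20%.

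**The plan's own figure.** The documents give no power or precision figure for safety. Their only figure is the 90 per group for efficacy. Read as a comparison of 60% with 30%, two-sided 0.05 and 80% power:

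n = [1.96·√(2·0.45·0.55) + 0.8416·√(0.6·0.4 + 0.3·0.7)]² / 0.30² = (1.379 + 0.565)² / 0.09 = 42 per arm.

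Dropout of 20% to 25% raises this to 42/0.80 = 53 or 42/0.75 = 56, not 90. A calculation on means or counts cannot be checked, because no SD or baseline rate is stated. This does not affect what follows, which takes 90 per arm as given.

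**Power of the safety test.** With p̄ the mean of the two rates,

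power ≈ Φ{ [√n·|p₁ − p₂| − 1.96·√(2p̄(1 − p̄))] / √(p₁(1 − p₁) + p₂(1 − p₂)) }.

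- 5% vs 10%: (0.4743 − 1.96·0.3725)/0.3708 = −0.690, power 24.5%, miss rate 75.5%.
- 10% vs 20%: (0.9487 − 1.96·0.5050)/0.5000 = −0.082, power 46.7%, miss rate 53.3%.

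Exact binomial enumeration at 90 per arm gives these miss rates:

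| Test | 5% vs 10% | 10% vs 20% |
|---|---|---|
| Pearson, uncorrected | 76.0% | 53.1% |
| Yates-corrected | 85.1% | 60.7% |
| Fisher exact | 82.9% | 60.3% |

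The SAP does not say whether a continuity correction is used; the uncorrected test is the most favourable of the three. If all 198 subjects whom SAP 5.2 plans to screen were randomized (99 per arm), the uncorrected test would still miss 73.3% and 48.7%. For 80% power the test would need about 435 per arm (5% vs 10%) or 199 per arm (10% vs 20%).

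**What an interval would add.** Newcombe 95% intervals for the risk difference, 90 per arm:

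| Affected, active vs placebo | Chi-square p | Difference (95% CI), points |
|---|---|---|
| 9 vs 9 | 1.0 | 0 (−9.2 to +9.2) |
| 9 vs 5 | 0.27 | +4.4 (−3.8 to +13.0) |
| 18 vs 9 | 0.060 | +10.0 (−0.5 to +20.5) |

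For 9 vs 5, the pooled rate is 14/180 = 0.0778, z = 0.0444/√(0.0778·0.9222·2/90) = 1.11 and p = 0.27. The Wilson limits are 0.0535 to 0.1792 (active) and 0.0240 to 0.1235 (placebo). The lower limit is 0.0444 − √(0.0465² + 0.0680²) = −0.038, and the upper limit is 0.0444 + √(0.0792² + 0.0316²) = +0.130.

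All three rows are non-significant at 5%. The last is an observed doubling.

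**The case against.** The best defence is that the plan already gives most of what is needed. The tables show numerators and percentages, so anyone can form the risk difference and calculate an interval. Low power for uncommon events is common to trials of this size, and an interval does not change it. Larger effects are not out of reach: an increase from 5% to 15% would be detected in 63% of trials at 90 per arm. All of this stands, and it limits the point to reporting.

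It could also be argued that SAP 7.4.2 promises a 95% interval in every case. That sentence follows a closed list: exacerbations, episode duration, antibiotic need, admissions and their duration, immunology, quality of life and costs. Adverse events are not on it, and the section is headed as secondary efficacy.

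Three stronger readings are tempting, and the documents do not support them.

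- A reader might infer that a non-significant test will stand as the trial's safety result, particularly as protocol 3.5 already claims that the product brings no added risk. No section says so. The 0.05 level is set for efficacy, and SAP 7.1 disclaims significance levels altogether. That disclaimer carries limited weight, since the next sentence concerns a histamine measure that is not an endpoint here. Protocol 3.5 is background and not an interpretation rule.
- A reader might apply the 20% to 25% dropout and work with about 70 per arm, which raises the miss rate for 5% vs 10% to about 80%. Dropouts who were dosed stay in the safety set, so 90 is the right denominator.
- A reader might infer that Holm will raise the bar for declaring harm. SAP 7.1.5 is conditional: "If multiple comparisons are needed, Holm adjustment for multiple comparisons will be used". It adds that multiple comparisons will be avoided except as exploratory work. Nothing applies the adjustment to adverse-event terms, and any family size would be invented.

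**Conclusion.** The point holds as a reporting gap. For adverse-event proportions, the only planned between-group inference is a chi-square test, with no effect estimate or interval beside it. At 90 per arm that test misses an assumed doubling in about 76% of trials (from 5%) or about 53% (from 10%), and more often with a continuity correction or Fisher's test. These figures assume a two-sided 5% level and event rates that the documents do not give. They show that non-significance would be weak evidence; they do not show that the product causes harm or that the sponsor will misread the result. No primary efficacy conclusion depends on this. It is a cheap improvement.

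**What to change.** In SAP 7.5 and protocol 10.1, replace the chi-square rule for adverse-event proportions with text along these lines:

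*For any AE, any SAE, any related AE, AEs leading to withdrawal, and local reactions, the difference in the proportion of subjects affected (active minus placebo) will be reported with a 95% confidence interval (Newcombe method). A non-significant difference will not be taken as evidence of safety; conclusions will refer to the interval.*

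Keep the descriptive tables by System Organ Class and Preferred Term. While editing, reconcile SAP 5.1.1, which asks for a dose of MV-130 in one sentence and includes all randomized subjects in the next, so that the denominator is clear.

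The cost is a wording change and one extra set of table columns, with no new data. The downside for the sponsor is that the report must show how much excess risk the data still allow.
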